#### **4.5.1.10 Apathy Evaluation Scale**

The AES is an 18-item assessment of apathy, including overt behavior, cognitive aspects of motivation, and emotional responsivity. Each item is scored on a 4-point Likert scale, from 1 ("Not at all") to 4 ("A lot").

A total score is created by summing the 18 items (scores range from 18 to 72; 3 of the items [item 6 "little effort", item 10 "Tell me what to do" and item 11 "Less concern than should be"] are reverse scored), with higher scores indicating greater apathy.

Missing values will not be replaced and total score derived only if all items are present. The assessment is considered completed if there are no missing items.

Descriptive tables will be provided as described in Section 4.5.1 and Table 2 for the patients and study companion versions for the overall score (as continuous variable) at baseline.

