4.5.10.11 Apathy Evaluation Scale

The AES is an 18-item assessment of apathy, including overt behavior, cognitive aspects of motivation, and emotional responsiveness. Each item is scored on a 4-point Likert scale, from 1 ("Not at all") to 4 ("A lot"). A total score is created by summing the 18 items (scores range from 18 to 72; 3 items are reverse scored), with higher scores indicating greater apathy. The AES takes approximately 10 minutes to complete and will be completed by the patient and study companion (if available) at clinic visits.

4.5.10.12 Neuro-Qol Cognition Function Short Form, Version 2

The Neuro-Qol Cognition Function Short Form contains 8 items (including "trouble concentrating" and difficulty "learning new tasks or instructions"), each assessed using a 5-point Likert scale, where lower scores indicate greater difficulty (4 items) or greater frequency (4 items). The raw sum score is converted to a T-score distribution (mean=50, SD=10). The Neuro-Qol Cognition Function Short Form takes approximately 5 minutes to complete and will be completed by the patient at clinic visits.

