### **Changes from Version 2 to Version 3**

The changes were mainly done to address identified inconsistencies or to increase clarity of the paragraphs.

Section 4.4 clarified further definition of baseline for clinical assessments with multiple predose measurements and for companion assessments.

Sections 4.5.1.6 and 4.5.1.7 corrected the value of the higher score and, as in section 4.5.1.12, corrected the definition of the direction of worsening /improvement for the change from baseline.

In Table 3 “country” was added as covariate where was previously omitted in error.

Section 4.7.3 and 4.7.3 corrected sentence on the use of local ranges for labs values.

Section 4.7.7 changed to aligned CSSR “Improvement on Suicidal ideation” derivation with the other studies in the program.

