### **2.2.3 Exploratory Endpoints**

- CGI-S: Clinical Global Impression–Severity
- CGI-C: Clinical Global Impression–Change
- PGI-S: Patient Global Impression–Severity
- PGI-C: Patient Global Impression–Change
- AES: Apathy Evaluation Scale
- EQ-5D-5L: Euro Qol 5 Dimension 5 level Questionnaire
- SMDSS: Symptoms of Major Depressive Disorder Scale
- WHODAS 2.0: World Health Organization Disability Assessment Schedule 2.0 (12 items scale)
- WPAI: Work Productivity and Activity Impairment
- HD-SDI: Huntington's Disease Speaking Difficulty Item
- MoCA: Montreal cognitive assessment (baseline only)
- Neuro-Qol Cog Func: Neuro Qol Cognitive Function Short form
- Roche HD mobile app digital endpoints:
  - Chorea
  - Speed tapping
  - Symbol digit modality test (SDMT)
  - Stroop Word Reading Test (SWT)
  - 2 minute walking
  - U turn
  - Balance test
  - Draw a shape

Additional digital endpoints may be considered.

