#### 4.5.1.15 Summary of Outputs for Describing the Longitudinal Changes Over Time

Table 2 Overview of Planned Outputs to Describe Parameter Longitudinal Changes Over Time

Parameter	Output Presentation			Data Type			Time points	MMRM Performed
	Plot	Table	Listing	Absolute	Change	%Change		
mHTT	Y	Y		Y	Y	Y	All available	Yes
CSF Biomarkers §	Y	Y		Y	Y	Y	All available	Yes
Plasma NFL	Y	Y		Y	Y	Y	All available	Yes
BSI	Y	Y			Y*	Y #	All available	Yes
normalized BSI	Y	Y			Y*	Y #	All available	Yes
BSL MRI Volume		Y		Y			BSL	No
BSL normalized MRI Volume		Y		Y			BSL	No
UHDRS +	Y	Y		Y	Y	Y	All available	Yes, except for IS
CGI-S		Y		Y	Y	Y	All available	No
CGI-C		Y			Y*		All available	No
PGI-S		Y		Y	Y	Y	All available	No
PGI-C		Y			Y*		All available	No
WHODAS 2.0		Y		Y	Y		All available	No
AES		Y		Y	Y		All available	No
Neuro-Qol Cog. Funct.		Y		Y	Y		All available	No
SMDDS		Y		Y	Y		All available	No
EQ-5D-5L (VAS only)		Y		Y	Y	Y	All available	No

Molecule: Not applicable—F. Hoffmann-La Roche Ltd

28/Statistical Analysis Plan BN40422

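### SAP 4.5.1.10 reverse-scores three Apathy Evaluation Scale items whose labels express apathy, yet reads a higher total as greater apathy

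*SAP*

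**What the plan says.** SAP 4.5.1.10 sets the response coding for the whole scale: "Each item is scored on a 4-point Likert scale, from 1" for not at all, up to 4 for a lot. The total is the sum of 18 items, with a stated range of 18 to 72. The section names the items to be flipped: "item 6 'little effort', item 10 'Tell me what to do' and item 11 'Less concern than should be'] are reverse scored". It then gives the direction of the total, so that three items "are reverse scored), with higher scores indicating greater apathy". No recoding of the other 15 items is mentioned.

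Protocol 4.5.10.11 gives the same rule without naming items: "3 items are reverse scored), with higher scores indicating greater apathy".

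SAP 2.2.3 lists the scale among the exploratory endpoints ("AES: Apathy Evaluation Scale"). SAP Table 2, "Overview of Planned Outputs to Describe Parameter Longitudinal Changes Over Time", plans AES tables of absolute values and change at all available timepoints, with no plot and no MMRM. SAP 4.5.1.10 covers both the patient and the study companion versions, but says the tables are "for the overall score (as continuous variable) at baseline".

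**The concern.** Reverse scoring exists to make every item point the same way as the total. Here the total is said to rise with apathy, so the items to reverse should be those on which a high answer means less apathy. The three named items are the opposite: making little effort, needing to be told what to do, and being less concerned than one should be all describe an apathetic person. Reversing them makes them work against the total.

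If a programmer follows the text, the patient and companion AES totals are wrong on three items at best. At worst the whole scale is upside down, and worsening apathy would appear in the change tables as a falling score, read as improvement. The stated range gives no warning, because 18 to 72 is the range of the total whichever way it points.

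**Working it through.** **Inputs, all from SAP 4.5.1.10.** 18 items; raw coding 1 to 4; items 6, 10 and 11 reversed; higher total means greater apathy. A reversed item scores 5 − raw.

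**Plan's own figure.** 18 × 1 = 18 and 18 × 4 = 72, so the stated range reproduces. It does not depend on direction.

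**The three named items alone.** A respondent who fully endorses apathy answers 4 on each. Left as answered they add 3 × 4 = 12. Reversed they add 3 × (5 − 4) = 3. The loss is 9 points, and 9/54 = 17% of the range (72 − 18 = 54).

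**Whole scale.** The wording of the other 15 items is not in the documents, so let k of them (0 to 15) be worded as apathy and 15 − k as motivation. Under the SAP rule:

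- Full apathy: 4k + 1(15 − k) + 3(5 − 4) = 18 + 3k
- No apathy: 1k + 4(15 − k) + 3(5 − 1) = 72 − 3k
- Separation (full minus none): 6k − 54

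| k | Full apathy | No apathy | Separation |
|---|---|---|---|
| 0 | 18 | 72 | −54 (fully inverted) |
| 5 | 33 | 57 | −24 |
| 8 | 42 | 48 | −6 |
| 9 | 45 | 45 | 0 |
| 10 | 48 | 42 | +6 |
| 15 | 63 | 27 | +36 (36/54 = 67%) |
| Correctly aligned score, any k | 72 | 18 | +54 |

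For no k does a fully apathetic respondent reach 72. The conclusion does not hang on the least explicit label. If item 10 were in fact worded as motivation, its reversal would be right, but items 6 and 11 would still cap full apathy at 15 × 4 + 4 + 2 × 1 = 66.

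**Is it repaired elsewhere?** Protocol 4.5.10.11 repeats the rule and names no items. The SAP amendment rationale for version 3 "corrected the definition of the direction of worsening /improvement for the change from baseline", but for Sections 4.5.1.6, 4.5.1.7 and 4.5.1.12, not for the AES section. Table 2 gives no scoring.

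**Separate timing slip.** SAP 4.5.1.10 limits the AES tables to baseline. Table 2 plans change at all available timepoints, and Protocol Appendix 3 schedules the scale at baseline and postbaseline clinic visits.

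**The case against.** The strongest reply is that reverse scored may be loose shorthand for keyed opposite to the other 15. If those 15 are recoded and these three kept as answered, full apathy scores 72, no apathy scores 18, and the stated direction holds. On that view the text is under-specified and the programmed score may be right. This could be what was intended, but it requires a recoding of 15 items that neither document states, and it contradicts the plain statement of which items are reversed.

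Several narrower points stand. The documents give only short labels for three items and nothing for the rest, so the size of the error cannot be fixed, and the intermediate values of k show sensitivity to an unknown rather than a likely result. If k = 0, spread and size of change are preserved and only the sign is wrong. Unlike the global severity scales in 4.5.1.6 and 4.5.1.7, AES has no improvement/worsening categories, so no patient would be misclassified in a planned output. The version 3 log shows only that the AES text was not among the listed corrections, not that its scoring went unreviewed. The protocol sentence is not contradictory by itself, since it names no items; the conflict comes from the SAP's labels. These points limit the consequence and leave the contradiction in place.

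**Conclusion.** The concern holds. Taken literally, the coding, the reversal list and the direction statement in SAP 4.5.1.10 cannot all be right, whatever the wording of the other 15 items. This rests on reading the three labels as expressing apathy and on no unstated recoding of the captured values.

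The size runs from three misaligned items (9 points of 54 at the extreme) to complete inversion. Inversion is the reading that the choice of only these three items implies, but confirming it needs the instrument itself. The reach is small: AES is exploratory, shown only in tables without MMRM, and absent from the Table 3 association models. No primary or secondary result is affected, and a wrong total can be re-derived from the same item data. It should be corrected before the AES tables are programmed.

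**What to change.** Check the wording of all 18 items against the instrument version in use, for patient and companion forms, and write the derivation item by item in SAP 4.5.1.10. Then:

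- If the other 15 items are worded as motivation, either reverse those 15 and leave items 6, 10 and 11 as answered, or keep the present reversal and state that a higher total means less apathy. In this case only, the first option equals 90 minus the current total, because each item's two scorings add to 5 and 18 × 5 = 90.
- If the other 15 are worded as apathy, drop the reversal of the three.
- If the wording is mixed, reverse exactly the items on which a high answer means less apathy.

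Make the sentence in Protocol 4.5.10.11 consistent with the result. Remove the restriction to baseline from SAP 4.5.1.10 so that it agrees with Table 2.

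The cost is SAP wording, one derivation line and one matching protocol sentence. A protocol change goes through the amendment route in Protocol 9.6, while SAP Section 1 lets SAP language supersede the protocol where specified, so the SAP can be corrected first. No new data are needed.

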#### **4.5.1.11 Neuro-QoL Cognition Function Short Form, Version 2**

The Neuro-QoL Cognition Function Short Form contains 8 items (including "trouble concentrating" and difficulty "learning new tasks or instructions"), each assessed using a 5-point Likert scale, from 1 to 5, where lower scores indicate greater difficulty (4 items) or greater frequency (4 items). The raw sum score is the sum of each individual item (range 8 to 40). The raw sum score is then converted to a T-score distribution (mean=50, SD=10). The conversion table from raw score to T score is provided in [Table 1](#).

For short forms with at least 5 items, if a patient skips one or more questions, a prorate score can be approximated if 4 (50%) of items have been answered. If enough responses are provided, the sum of the response scores from the items that were answered is multiplied by the total number of items in the short form and then divided by the number of items that were answered. If the result is a fraction, it should be rounded up to the nearest whole number. This is a pro-rated raw score. However, this prorated score should be used with caution as the advantages of IRT calibrations and their contribution to precision is lost in the process.

The pro-rated raw score is then converted to a normalized T score using the table below ([Table 1](#)).

**Table 1 Conversion table from raw score to T score**

Cognitive Function v2.0 8-item Short Form (Adult)					
Raw Score	T-Score	SE	Raw Score	T-Score	SE
8	17.3	4.3	25	39.9	2.6
9	20.4	3.8	26	40.9	2.6
10	22.6	3.5	27	41.9	2.6
11	24.4	3.3	28	42.9	2.6
12	25.9	3.1	29	43.9	2.7
13	27.3	3	30	44.9	2.7
14	28.6	2.9	31	46	2.7
15	29.8	2.8	32	47.1	2.7
16	30.9	2.7	33	48.3	2.8
17	32	2.7	34	49.6	2.8
18	33	2.6	35	50.9	2.9
19	34	2.6	36	52.4	3.1
20	35	2.6	37	54.2	3.3
21	36	2.6	38	56.3	3.7
22	37	2.6	39	59	4.2
23	37.9	2.6	40	64.2	5.7
24	38.9	2.6			

Source: <http://www.healthmeasures.net/score-and-interpret/calculate-scores/scoring-instructions> , [http://www.healthmeasures.net/images/neuro\\_qol/Neuro\\_QOL\\_Scoring\\_Manual\\_Mar2015.pdf](http://www.healthmeasures.net/images/neuro_qol/Neuro_QOL_Scoring_Manual_Mar2015.pdf).

Descriptive tables and plots for the T score (as continuous) will be provided as described in Section 4.5.1 and Table 2.

#### 4.5.1.12 Huntington's Disease—Speaking Difficulty Item

The HD-SDI is a single question assessing difficulty speaking over the past 7 days. It is assessed using a 5-point Likert scale, where higher scores indicate a greater frequency of difficulty.

The scale is not considered completed if there is no result available. There will be no imputation for missing data.

#### 4.5.1.13 Symptoms of Major Depressive Disorder Scale

The SMDDS is a newly developed, valid, and reliable self-report assessment of depression (McCarrier et al. 2016). It contains 16 items, measuring concepts such as sadness, irritability, worry, and sleep disturbance. Each item is assessed on a 5-point Likert scale, from "Not at all" (0), to "Extremely" (4) (9 items) and from "Never" to "Always" (7 items). Item scores from 15 of the items (the least severe of the two eating items is dropped) are summed to create a 0–60 score, where higher scores indicate more severe depressive symptomatology.

Missing values will not be replaced and total score derived only if all items are present. The assessment is considered completed if there are no missing items.

Descriptive tables and plots will be provided as described in Section 4.5.1 and Table 2 for the overall score (as continuous variable).

#### **4.5.1.14 EuroQol 5-Dimension, 5-Level Questionnaire**

The EQ-5D-5L is a validated self-report health status questionnaire used to calculate a health status utility score for use in health economic analyses (EuroQol Group 1990; Brooks 1996; Herdman et al. 2011; Janssen et al. 2013). There are two components to the EQ-5D-5L: a 5-item health state profile that assesses mobility, self-care, usual activities, pain/discomfort, and anxiety/depression, as well as a visual analogue scale (VAS) (range from 0 worst - to 100 best) that measures health state. Published weighting systems allow for creation of a single composite score of the patient's health status (Index score) from the 5-item scores (i.e., does not include the VAS).

Missing values will not be imputed, the composite score will only be computed if all questions have been answered.

The Index score will be used for informing pharmaco-economic evaluations. The VAS score will be used to assess HRQoL. The EQ-5D-5L index score will not be reported in the study CSR, VAS score will be summarized (as continuous variable) by study visit as described in Section 4.5.1 and Table 2.

The EQ-5D-5L will be completed both by the patient (about him/herself) and by the study companion (if available, about him/herself) at baseline and post-baseline clinic visits on an electronic device. In addition, it will be completed weekly by the patient remotely on the Roche HD mobile app and weekly by the study companion remotely on an electronic device.

#### 4.5.1.15 Summary of Outputs for Describing the Longitudinal Changes Over Time

Table 2 Overview of Planned Outputs to Describe Parameter Longitudinal Changes Over Time

Parameter	Output Presentation			Data Type			Time points	MMRM Performed
	Plot	Table	Listing	Absolute	Change	%Change		
mHTT	Y	Y		Y	Y	Y	All available	Yes
CSF Biomarkers §	Y	Y		Y	Y	Y	All available	Yes
Plasma NFL	Y	Y		Y	Y	Y	All available	Yes
BSI	Y	Y			Y*	Y #	All available	Yes
normalized BSI	Y	Y			Y*	Y #	All available	Yes
BSL MRI Volume		Y		Y			BSL	No
BSL normalized MRI Volume		Y		Y			BSL	No
UHDRS +	Y	Y		Y	Y	Y	All available	Yes, except for IS
CGI-S		Y		Y	Y	Y	All available	No
CGI-C		Y			Y*		All available	No
PGI-S		Y		Y	Y	Y	All available	No
PGI-C		Y			Y*		All available	No
WHODAS 2.0		Y		Y	Y		All available	No
AES		Y		Y	Y		All available	No
Neuro-Qol Cog. Funct.		Y		Y	Y		All available	No
SMDDS		Y		Y	Y		All available	No
EQ-5D-5L (VAS only)		Y		Y	Y	Y	All available	No

Molecule: Not applicable—F. Hoffmann-La Roche Ltd

28/Statistical Analysis Plan BN40422

**Table 2 Overview of Planned Outputs to Describe Parameter Longitudinal Changes Over Time (cont.)**

Absolute=measured data at a given time point; BSL=Baseline

Change (%Change)=change from baseline from a given post-baseline measurement (expressed as a percentage)

\* BSI, CGI-C and PGI-C are already a measure of change thus the change is not derived as for the other variables)

‡ %Change for BSI is derived as  $\left( \frac{BSI}{baseline\ volume} \right) \cdot 100$

§ CSF Biomarkers will include NFL, YKL-40 and Tau

+ The parameters considered are cUHDRS, its individual total raw score components as well the Independence Scale(IS), Maximal chorea score and Maximal chorea of upper limb

#### **4.5.2 Relationship Between Selected Parameters**

The objective of this section is to investigate the relationship between selected pairs of parameters, e.g. CSF mHTT and cUHDRS, to assess:

- the prognostic value of baseline CSF mHTT for the change in cUHDRS at pre-specified time-points
- the relationship between change in CSF mHTT and change in cUHDRS at pre-specified time-points

Both descriptive statistics (scatter plots) and statistical modelling will be applied to the data. All analyses in this section will be based on the ITT analysis population.

##### **4.5.2.1 Descriptive Analyses**

Scatter plots between selected pairs of continuous variables will be presented based on data types shown in [Table 3](#) for X (main predictor, e.g. CSF mHTT) and Y (response, e.g. cUHDRS) variables at each time point separately. At each time point only those data from visit occurring  $\pm$  56 days from the scheduled visit will be used.

##### **4.5.2.2 Model-based Analyses**

In order to model the relationship between a continuous response variable (e.g. the change in cUHDRS) and a main predictor (e.g. change in CSF mHTT) at a given time-point, a linear regression model (LRM) will be used. At each time point only those data from visit occurring  $\pm$  56 days from the scheduled visit will be used.

The full list of analyses which will be considered, together with specifications about additional covariates to account for, is provided in [Table 3](#). Additional analyses, not listed in this SAP, may be conducted to better understand any safety concern which may arise.

Least squares means (LSM) estimates, at each time-point, for the slope of the main predictor (X-variable in [Table 3](#)) along with corresponding standard error, 95% CI and unadjusted p-value will be presented. The estimated effect represents the effect of the main predictor on the response adjusted for all other covariates in the model. Distributional assumptions underlying the model used for analysis will be examined to gain confidence that the model assumptions are reasonable and where needed, sensitivity analyses will be performed.

The procedure that will be used to fit linear regression in SAS is as follows:

```
proc mixed data=dataname plots=all;
class
model y-variable= x-variable + {additional covariates in Table 3} /ddfmi=kr cl;
ods output solutionf=outputname;
run;
```

In addition to [Table 3](#), scatter plots and Spearman correlations will be calculated among all baseline fluid biomarkers at baseline. Similar analyses will be performed for CAG and CAP with baseline fluid biomarkers, baseline CSF mHTT and baseline cUHDRS (including individual components). CAP is defined by the product of (CAG – 33.66) by baseline age.

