4.6 PATIENT, STUDY, AND SITE DISCONTINUATION

4.6.1 Patient Discontinuation

Patients have the right to voluntarily withdraw from the study at any time for any reason. In addition, the investigator has the right to withdraw a patient from the study at any time. Reasons for withdrawal from the study may include, but are not limited to, the following:

- Patient withdrawal of consent
- Study termination or site closure
- Patient non-compliance, defined as failure to comply with protocol requirements as determined by the investigator or Sponsor

Every effort should be made to obtain information on patients who withdraw from the study. The primary reason for withdrawal from the study should be documented on the appropriate eCRF. Patients will not be followed for any reason after consent has been withdrawn. Patients who withdraw from the study may be replaced, particularly if withdrawal is early-on (e.g., within first 6 months).

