6.3 PRIMARY ANALYSES

The primary objective of this study is to investigate whether baseline CSF mHTT is a predictor of the change from baseline to 15 months for the following variables:

- Clinical endpoints (cUHDRS, TFC, TMS, SDMT, SWR, and IS)
- CSF and blood biomarkers
- Brain imaging (MRI)

Initially, a linear model will be used to evaluate the association between each response variable (e.g., change from baseline to 15 months in cUHDRS) and baseline CSF mHTT without adjustment for any baseline characteristics.

The same model will then be considered again, adjusting for baseline level of the response variable (e.g., baseline cUHDRS), baseline CSF mHTT levels, CAG, and baseline CAP (the latter defined as the product of age at baseline by [CAG—33.66] (Zhang et al. 2011). A sensitivity analysis to evaluate the impact of additional baseline characteristics (e.g., gender, education level) may be performed.

Other approaches may be used in the case of severe multicollinearity, which would result in model instability.

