### **2.2.1 Primary Endpoints**

The primary objective of this study is to examine the predictive value of baseline cerebrospinal fluid (CSF) mHTT levels on measures of disease progression using the following endpoints:

- Change from baseline in the following clinical endpoints at 3, 9, and 15 months: composite Unified Huntington's Disease Rating Scale (cUHDRS), Total Functional Capacity Scale (TFC), Total Motor Scale (TMS), Symbol Digit Modalities Test (SDMT), Stroop Word Reading (SWR) Test, and Independence Scale (IS)
- Change from baseline in biomarkers of neuronal injury (e.g., CSF neurofilament light chain [NfL] and tau) at 3, 9, and 15 months
- Change from baseline in brain atrophy endpoints (e.g., whole brain volume decline, caudate volume decline) as determined by brain MRI, at 3, 9, and 15 months

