#### **4.5.1.3.5 cUHDRS**

Based on the aforementioned assessments, the following formula is used to derive the cUHDRS where TFC, TMS, SDMT and SWRT are the raw total scores of each assessment:

$$\text{cUHDRS} = \left( \frac{\text{TFC} - 8.8}{2.8} \right) - \left( \frac{\text{TMS} - 34.4}{17.4} \right) + \left( \frac{\text{SDMT} - 25.2}{12.4} \right) + \left( \frac{\text{SWRT} - 58}{21.2} \right) + 10.0$$

The cUHDRS will be derived only if each of the individual components is not missing. No imputation for missing values will be conducted. The minimum possible score is -3.06. The maximum is not defined.

Descriptive tables and plots as well results from the MMRM model will be provided as described in Section 4.5.1 and [Table 2](#) for cUHDRS, its individual components total raw scores, the 'maximal chorea in upper limb' item (left and right; from TMS) and the 'maximal chorea score'.

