**Table 3 Overview of Planned Outputs to Describe the Association Between Selected Pairs of Parameters at Final analysis.**

Paired Variables	Data Type				Time points	Additional covariates in statistical models		
	X-variable		Y-variable					
	Absolute	Change	Absolute	Change				
X=mHTT, Y=Clinical Endpoints §	Y		Y		X & Y=BSL	BSL-Age, CAG, CAP, Country		
	Y			Y	X=BSL, Y=15M	BSL- Clin.endp, BSL-Age, CAG, CAP, Country		
		Y		Y	X=3M, 9M, 15M, Y=15M	BSL- Clin.endp, BSL-mHTT, BSL-Age, CAG, CAP, Country		
X= CSF Biomarkers, Y=Clinical Endpoints	Y		Y		X & Y=BSL	BSL-Age, CAG, CAP, Country		
	Y			Y	X=BSL, Y=15M	BSL- Clin.endp, BSL-Age, CAG, CAP, Country		
		Y		Y	X=3M, 9M, 15M, Y=15M	BSL- Clin.endp, BSL-CSF.Biom, BSL-Age, CAG, CAP, Country		
X=mHTT, Y=CSF Biomarkers *	Y		Y		X & Y=BSL	BSL-Age, CAG, CAP		
	Y			Y	X=BSL, Y=15M	BSL- CSF.Biom, BSL-Age, CAG, CAP		
		Y		Y	X & Y=3M, 9M, 15M	BSL-CSF.Biom, BSL-mHTT, BSL-Age, CAG, CAP		
X=CSF-NfL, Y=Plasma-NfL	Y		Y		X & Y=BSL	None		
		Y		Y	X & Y=3M, 9M, 15M	None		
X=mHTT, Y=normalised MRI	Y		Y		X & Y=BSL	BSL-Age, CAG, CAP		
X=CSF-Biom Y=normalised MRI	Y		Y		X & Y=BSL	BSL-Age, CAG, CAP		
X=mHTT, Y=BSI *	Y			Y (%-change)	X=BSL, Y=3M, 9M, 15M	BSL-Age, CAG, CAP		
		Y		Y (%-change)	X=3M, 9M, 15M, Y=15M	BSL-mHTT, BSL-Age, CAG, CAP		
X=CSF-Biom, Y=BSI *		Y		Y (%-change)	X=3M, 9M, 15M, Y=15M	BSL-Biom, BSL-Age, CAG, CAP		

**Table 3 Overview of Planned Outputs to Describe the Association Between Selected Pairs of Parameters at Final analysis (cont.)**

BSL= baseline; BSI= boundary shift integral; mHTT=mutant huntingtin protein; CAP= =(CAG-33.66)\* AGE\_BASELINE; CSF= cerebrospinal fluid; NfL= neurofilament light chain; MRI= magnetic resonance imaging.

§ Clinical Endpoints will include cUHDRS, TFC, TMS, SDMT and SWR

+ CSF Biomarkers will include NFL, YKL-40 and Tau

‡ MRI Volume

\* BSI is already a measure of change thus the change is not derived.

In case of an interim analysis (see Section 4.9) the analyses will be based on the available data (e.g. up to 9 months) by the clinical cutoff date.

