### Mixed-Model Repeated Measures Technical Details

The advantage of mixed-model repeated measures (MMRM) analysis is that it takes into account the fact that measurements from the same patients are correlated and also that all available data are used without eliminating individuals without complete information. The following points will be considered during MMRM model fitting;

- The Kenward and Roger method for approximating the denominator degrees of freedom and correcting for bias in the estimated variance-covariance of the fixed effects will be used.

In the event the model fails to run using the KR method, then the residual method will be used instead.

- For modelling change from baseline with a limited number of post-baseline time points (3M, 9M and 15M) an Unstructured covariance structure for the R matrix will be used by specifying 'type=UN' on the REPEATED line.

In the event that this model fails to converge, alternative correlation structures may be considered. Akaike's Information Criteria (AIC) will be used to assist with the selection of covariance structure.

- For modelling change from baseline with many post-baseline time points (>3), a Heterogeneous Toeplitz covariance structure for the R matrix will be used by specifying 'type=TOEPH' on the REPEATED line.

In the event that this model fails to converge, alternative correlation structures may be considered. Akaike's Information Criteria (AIC) will be used to assist with the selection of covariance structure.

Distributional assumptions underlying the model used for analysis will be examined to gain confidence that the model assumptions are reasonable and where needed, sensitivity analyses will be performed.

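### Baseline-mHTT slopes for clinical endpoints and CSF biomarkers rest on Month 15 completers only; add a repeated-measures model with mHTT and every covariate crossed with visit

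*SAP*

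**What the plan says.** - **Target.** Protocol 6.3 sets out to "investigate whether baseline CSF mHTT is a predictor of the change from baseline to 15 months". SAP 2.2.1 lists the primary endpoints more widely: "Change from baseline in the following clinical endpoints at 3, 9, and 15 months". The two earlier changes are therefore named primary endpoints too.
- **Model.** SAP 4.5.2.2 relates response to predictor thus: "at a given time-point, a linear regression model (LRM) will be used". It restricts the data: "At each time point only those data from visit occurring" up to 56 days either side of schedule. The SAS call has no REPEATED or RANDOM statement.
- **Visits.** In SAP Table 3, clinical endpoints and CSF biomarkers are regressed on baseline mHTT at Month 15 only. BSI has "X=BSL, Y=3M, 9M, 15M", which means three separate single-visit fits.
- **Missing values.** For cUHDRS (SAP 4.5.1.3.5): "No imputation for missing values will be conducted". SAP 4.8 takes the same line for CSF biomarkers, apart from values below quantitation.
- **Mean change.** SAP 4.5.1 uses an MMRM, and Appendix 4 gives as one of its advantages that "all available data are used without eliminating individuals without complete information". Its covariates are the endpoint's own baseline, CAG, age, CAP, country (outcome assessments only) and visit, all as main effects.
- **Withdrawal.** Protocol 4.6.1: "Patients who withdraw from the study may be replaced, particularly if withdrawal is early-on (e.g., within first 6 months"). Neither document gives a dropout rate.

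**The concern.** The plan's own argument for a repeated-measures model is that incomplete patients stay in. That argument is applied to the description of mean change but not to the mHTT slope, which is the primary question. A patient seen at Months 3 and 9 but not within the Month 15 window is used in the first analysis and dropped from the second.

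Two things are at stake. One is precision, in a cohort of about 100. The other is attenuation: if patients who have already declined more are likelier to lack a Month 15 value, the completers are selected on something close to the outcome.

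Loss of this kind does not require withdrawal. SAP 4.5.1.3.3 and 4.5.1.3.4 leave SDMT and SWR missing when a patient cannot do the task, and cUHDRS is then missing as well.

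**Working it through.** **1. Who contributes.** Month 15 is Day 421, so the window is 421 − 56 = Day 365 to 421 + 56 = Day 477. The plan has no precision or power figure to reproduce. Its sample size is a 2:1 match to 46 patients (2 × 46 = 92), under a ceiling of about 100. With an assumed fraction d lacking an in-window value, the regression uses N(1 − d) patients and its standard error rises by 1/√(1 − d):

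| d (assumed) | n of 100 | n of 92 | SE factor |
|---|---|---|---|
| 10% | 90 | 83 | 1.054 |
| 20% | 80 | 74 | 1.118 |
| 30% | 70 | 64 | 1.195 |

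**2. Does another provision rescue the slope?** The MMRM has no mHTT term for progression endpoints. The random-slope model in SAP 4.5.1 is triggered by visit delay and has no such term either. The sensitivity analyses mentioned in 4.5.2.2 concern distributional assumptions. Replacing a withdrawn patient restores the count, not the lost trajectory.

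**3. Bias.** Simulation with 4,000 runs per scenario and n = 100. All inputs are assumptions:
- Standardised baseline log-mHTT, with one covariate correlated 0.5 with it (effect −0.2).
- Linear decline with random-slope SD 0.8 and visit error SD 0.6, so the Month 15 residual variance is 0.64 + 0.36 = 1.
- Month 9–15 residual correlation 0.384/√0.5904 = 0.50.
- Loss after Month 9; where it is not random, log-odds 1.5 per SD of its driver.

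The joint model has visit-specific coefficients for mHTT and for the covariate. Mean estimates for a true slope of −0.30 at 10/20/30% loss:

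| Loss depends on | Month 15 regression | Joint model |
|---|---|---|
| nothing (random) | −0.301/−0.302/−0.300 | −0.301/−0.301/−0.300 |
| baseline mHTT only | −0.298/−0.299/−0.302 | −0.299/−0.298/−0.302 |
| Month 9 change | −0.287/−0.276/−0.274 | −0.299/−0.296/−0.299 |
| Month 15 change itself | −0.270/−0.252/−0.242 | −0.278/−0.263/−0.255 |

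- **Month 9-driven loss.** The attenuation is 0.013/0.300 = 4%, 0.024/0.300 = 8% and 0.026/0.300 = 9%. Against empirical SDs of 0.124, 0.129 and 0.140 this is 0.10, 0.19 and 0.19 standard errors. Coverage of the 95% CI stays at 94–95%. Other assumed settings with the same n and true slope reach 14% at the upper end. There, 0.14 × 0.30 = 0.042, about 0.3 of an SE of 0.14.
- **Loss driven by the unseen Month 15 change.** The regression is 10/16/19% too small, with coverage 94/93/92%. The joint model is still 7/12/15% too small.
- **True slope zero.** There is no material bias under any of the four mechanisms.

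**4. Precision under random loss.** If Months 3 and 9 are observed, the joint model reduces slope variance by about d × R², where R² is that of Month 15 on the earlier changes, given the covariates. With Month 9–15 correlation 0.6 to 0.8, this runs from 0.20 × 0.36 = 7% to 0.30 × 0.64 = 19%. If Month 3 is also correlated 0.8 with both later visits, R² = 2 × 0.64/1.8 = 0.71 and the reduction at 30% loss is 0.30 × 0.71 = 21%. In the simulation above (correlation 0.50), the ratios (0.127/0.131)² and (0.139/0.144)² give 6% and 7%.

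**5. Which joint model?** With complete data, unstructured covariance and the same covariates given their own coefficient at every visit, the repeated-measures fit equals visit-by-visit least squares. It therefore reproduces the Table 3 Month 15 slope. The SAP 4.5.1 MMRM does not have this property, because each covariate has one coefficient shared by all visits. A check with **no dropout** assumed a true slope of −0.30 and a covariate correlated 0.3–0.5 with mHTT, whose effect grows linearly to −0.2 or −0.3. The Month 15 regression gave −0.29 to −0.30. The 4.5.1 MMRM plus mHTT and mHTT × visit gave −0.32 to −0.43, about 8–43% away from zero. Crossing the covariate with visit removed the bias.

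**The case against.** The strongest reply is that little turns on this. The study is declared exploratory with no formal test. The bias under Month 9-driven loss is a fraction of a standard error, and interval coverage barely moves. The ±56-day window is eight times the protocol's ±7 days and keeps moderately late visits. Access to the open-label extension comes after the observational period, which may favour retention. SAP 4.2 and 4.2.1 summarise discontinuations and COVID-19-related missed assessments, and 4.5.3 leaves room for further analyses. All of this stands and limits the weight of the point. It does not supply a pre-specified analysis that uses the discarded data, and the slope with its interval is what the study is meant to deliver.

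A reader might also infer more than the documents support:
- **That the slope is biased whenever faster decliners leave.** It is not if the true slope is zero, or if the model's covariates explain who leaves.
- **That every primary domain is analysed at Month 15 only.** BSI is also regressed at Months 3 and 9, although its Month 15 fit drops the same patients.
- **That the protocol anticipates substantial withdrawal.** Section 4.6.1 only permits replacement, so the 10–30% used here is an assumption.

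**Conclusion.** The point holds as a conditional and modest weakness. For clinical endpoints and CSF biomarkers, the baseline-mHTT slope is a Month 15 complete-case estimate, and Month 3 and 9 data already collected are left unused.

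- **Bias:** roughly 4–14% toward zero at an assumed 10–30% loss driven by Month 9 change. It requires a non-zero slope and loss related to decline beyond the covariates, and it is small against the standard error.
- **Precision:** if loss is random, the only cost is slope variance that a joint model would lower by roughly 7–20% at 20–30% loss.

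These sizes rest on assumed dropout, correlations and effect size, because the documents state none of them. No error rate is affected. It would be tempting to conclude that the Table 3 regression should be discarded, or that one extra term in the existing MMRM is enough. Neither follows: the regression remains a valid completer analysis, and the MMRM with main-effect covariates can mislead even with no dropout.

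**What to change.** For the baseline-mHTT rows of Table 3, add a repeated-measures model of the Month 3, 9 and 15 changes. Use unstructured covariance and Kenward–Roger degrees of freedom, as Appendix 4 already specifies for the MMRM. Include visit, baseline log-mHTT × visit, and **every** covariate listed for that row × visit: baseline endpoint, age, CAG and CAP, plus country where listed. Report the Month 15 mHTT slope with its 95% CI, and keep the single-visit regression beside it, labelled as the completer analysis. Apply the same to BSI with the covariates of its own row.

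The cost is SAP wording and some code, with no new data. The model is larger. For a clinical endpoint it has 3 visit intercepts, 5 × 3 = 15 slopes and 6 covariance parameters, plus 3 per country beyond the first. Country may therefore need pooling by region, which SAP 4.5.1 already allows for convergence problems. Patients without baseline mHTT still drop out. The repair is only partial if loss depends on the unseen Month 15 value; a delta-adjusted or pattern-based sensitivity analysis would be needed to explore that.
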